14.2. Sample Size, Accrual Time and Study Duration

A minimum of 6 and a maximum of 25 patients will be accrued. We anticipate that 3 patients will be enrolled and followed for the development of a DLT every 4-6 months, the time between determination of MTD and opening of the expansion cohort to be 2 months, and 1 patient per month would be enrolled during the expansion phase of the study. Thus, the enrollment period would be approximately 42 to 48 months.

14.3. Definitions of Endpoints and Analysis Plan

14.3.1 Patient Evaluability

All patients meeting the eligibility criteria who have signed a consent form and have begun treatment will be included in the analysis of the safety and clinical outcome data.

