2.4. Endpoints

2.4.1 Primary and Secondary

Primary:

1. Maximum tolerated dose (MTD): The maximum tolerated dose (MTD) is defined as the highest dose level among those under consideration where at most 1 of 6 patients develops a dose limiting toxicity and 2 or more of the 3-6 patients treated at the next higher dose level develop a dose limiting toxicity.
2. Safety profile: The maximum grade of each type of toxicity will be recorded for each patient. For each toxicity reported by dose level, the percentage of patients developing any degree of that toxicity as well as the percentage of patients developing a severe degree (Grade 3 or higher) due to treatment will be determined.

Secondary:

1. Progression free survival (PFS) defined as the time from study entry to the documentation of disease progression using IMWG criteria or death due to any cause.
2. Overall survival (OS) is defined as time from registration to death due to any cause.
3. Overall Response rate(ORR)
4. Duration of response, defined as the time from documented response to disease progression among those patients whose disease meets the IMWG criteria for disease response.
5. Safety Profile: CTCAE v5.0 will be used to grade and assign attribution to each adverse event reported.

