7.1. Definition of Dose-Limiting Toxicity (DLT)

Attributions should be made as possibly, probably, or definite.

Table 9 Dose limiting toxicities (DLT)

Toxicity	DLT Definition
Hematologic	Grade 4 thrombocytopenia or Grade 3 thrombocytopenia with bleeding or requirement for platelet transfusion.

	Grade 4 neutropenia lasting more than 5 days.
Other nonhematologic*	≥ grade 3 as per NCI Common Terminology Criteria for Adverse Events (CTCAE) version 5.0*
	Grade 4 febrile neutropenia
	≥ grade 3 hyperglycemia due to dexamethasone if it cannot be controlled with appropriate therapy
	Treatment delays ≥ 21 days for any non-hematologic or hematological toxicity
	Treatment related death
	Grade ≥ 3 thrombotic/embolic events including DVT
	Grade 4 nausea, vomiting and diarrhea

*except grade 3 nausea, vomiting, diarrhea that does not require tube feeding, total parenteral nutrition or prolonged hospitalization, diarrhea responsive to medical treatment, nausea or vomiting controlled with antiemetics, or transient electrolyte abnormalities that resolve < grade 1 within 48 hours

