7.3. Enrollment and determination of MTD

A minimum of 2 or a maximum of 6 patients will be accrued to a given dose level. Enrollment will begin with 3 patients accrued to dose level 1.

Dose de/escalation scheme for Dose 1:

- If none of the first 3 patients treated at dose level 1 develops a DLT during the first cycle of treatment, then the next cohort of 3 patients will be enrolled at dose level 2.
- If one of the first 3 patients treated at dose level 1 develops a DLT during the first cycle of treatment, then an additional cohort of 3 patients will be enrolled at the current dose level.
- If at most 1 of the 6 patients enrolled at dose level 1 develops a DLT during the first cycle of treatment, the next cohort of 3 patients will be treated at dose level 2.
- If 2 or more of the 6 patients enrolled at level 1 develops a DLT during the first cycle of treatment, enrollment will be halted, and the study team will discuss whether to

submit an amendment to reopen enrollment to a lower dose level.-

As of October 7, 2021, 3 patients have been enrolled onto dose level 2.

Dose de/escalation scheme for Dose 2:

- If none of the first 3 patients treated at dose level 2 develops a DLT during the first cycle of treatment, then the next cohort of 3 patients will be enrolled onto dose level 3.
- If one of the 3 patients treated at dose level 2 develops a DLT during the first cycle of treatment, then the next cohort of 3 patients will be enrolled at dose level 2.
 - If 2 or more of the 6 patients treated at dose level 2 develops a DLT then an additional 10 patients will be enrolled onto dose level 1 before completing enrollment.
- If 2 or more of 3 patients treated at dose level 2 develops a DLT during the first cycle of treatment, an additional 10 patients will be enrolled onto dose level 1 to further assess safety before completing enrollment.

Dose de/escalation scheme for Dose 3 (if applicable):

- If at most 1 of 6 patients treated at dose level 2 develops a DLT during the first cycle of treatment and 1 or fewer of the 6 patients treated at dose level 3 develops a DLT in the first cycle of treatment, then an additional 4 patients will be treated on dose level 3 before completing enrollment.

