- If at most 1 of 6 patients treated at dose level 2 develops a DLT during the first cycle of treatment and 2 or more of the 3-6 patients treated at dose level 3 develops a DLT during the first cycle of treatment, then an additional 7 patients will be enrolled onto dose level 2 before completing enrollment.
- If at most 1 of 6 patients treated at dose level 3 develops a DLT during the first cycle of treatment then an additional 4 patients will be enrolled onto dose level 3 before completing enrollment.
- If 2 or more of the 3-6 patients treated at dose level 3 develops a DLT during the first cycle of treatment then an additional 7 patients will be enrolled onto dose level 2 before completing enrollment.

8. Dose and Treatment Modifications

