14.1. Overview of the Study Design

This is a single-arm, open label, phase Ib study of Ibrutinib in combination with lenalidomide and dexamethasone in adult (age 18 years and older) patients with relapsed/refractory MM. A 3+3 phase I clinical trial design as described in Section 6.0 was chosen to determine the MTD of Ibrutinib in combination with lenalidomide given on days 1-21 of a 28-day cycle and dexamethasone given orally weekly. An expansion cohort of 10 patients will be treated at the MTD to gather additional safety and anti-tumor activity data.

As of April 15, 2021, 2 patients have been enrolled onto dose level 2.

- If none of the first 3 patients treated at dose level 2 develops a DLT, then the next cohort of 3 patients will be enrolled onto dose level 3 and biospecimen collection will begin for all subsequent patients enrolled.
- If one of the 3 patients treated at dose level 2 develops a DLT, then the next cohort of 3 patients will be enrolled at dose level 2 and correlative biospecimens will be collected from these patients.
 - o If 2 or more of the 6 patients treated at dose level 2 develops a DLT then an additional 10 patients will be enrolled onto dose level 1 so that a total of 10 patients will have provided biospecimens at the MTD. (Note: Total sample size will be 6 [from dose level 1] + 6 [from dose level 2] + 10 [for dose expansion] = 22. Biospecimens will be available for 10 patients treated at the MTD.)
- If 2 or more of 3 patients treated at dose level 2 has an DLT, an additional 10 patients will be enrolled onto dose level 1 to further assess safety and collect specimens for correlative aims. (Note: Total sample size will be 6 [from dose level 1] + 3 [from dose level 2] + 10 [for dose expansion] = 19. Biospecimens will be available for 10 patients treated at the MTD.)
- If at most 1 of 6 patients treated at dose level 2 develops a DLT and 2 or more of the 3-6 patients treated at dose level 3 develops a DLT, then an additional 7 patients will be enrolled onto dose level 2 so that a total of 10 patients will have provided biospecimens at the MTD. (Note: Total sample size will be 6 [from dose level 1] + 6 [from dose level 2] + 6 [maximum number anticipated on dose level 3] + 7 [for dose expansion] = 25. Biospecimens will be available for 10 patients treated at the MTD.)

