14.3.2 Statement for Primary Endpoint

The primary endpoint of the dose escalation portion of this phase I study is the MTD. The maximum tolerated dose is defined as the highest dose level among those tested where at most one out of 6 patients develops a DLT prior to the start of their second cycle of treatment and the next highest dose level is such that 2 or more patients among the maximum of 6 patients treated at that dose level developed a DLT prior to the start of their second cycle of treatment.

The primary endpoint of the expansion portion of this phase I study is the objective response rate. The objective response rate is the percent of patients who meet the International Myeloma Working Group Response Criteria for sCR, CR, VGPR, or PR on two consecutive evaluations at least 4 weeks apart among the patients who began study treatment. A 90% binomial confidence interval will be constructed for the overall objective response rate.

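### Eligibility is a condition for the safety analysis, so a treated patient later found ineligible can drop out of it; the dose-escalation counts also lack a DLT-evaluable rule

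*Combined protocol and SAP*

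**What the plan says.** **Analysis population.** Section 14.3.1 (Patient Evaluability) states: "All patients meeting the eligibility criteria who have signed a consent form and have begun treatment will be included in the analysis". The sentence goes on to name both safety and clinical outcome data. Section 14.3.2 takes the objective response rate "among the patients who began study treatment", with no eligibility condition. Section 2.4.1 makes the safety profile the second primary endpoint: "For each toxicity reported by dose level, the percentage of patients developing any degree of that toxicity", together with the percentage at grade 3 or higher.

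**Escalation counts.** Section 7.3 says: "A minimum of 2 or a maximum of 6 patients will be accrued to a given dose level". Its counts are of patients treated or enrolled at a level. For example: "If none of the first 3 patients treated at dose level 2 develops a DLT during the first cycle of treatment", then level 3 opens. Sections 7.2 and 14.3.2 define the MTD by at most one DLT in six patients before cycle 2 starts. I found no text that defines a DLT-evaluable patient, sets a minimum cycle 1 exposure or provides for replacement.

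**Related provisions.** Table 9 in 7.1 counts listed toxicities, treatment-related death and "Treatment delays ≥ 21 days for any non-hematologic or hematological toxicity" as DLTs. Section 8.3 lists other reasons for stopping, including progression, withdrawal and intercurrent illness. Section 10.5 captures all adverse events until 30 days after treatment stops. The notes in 14.1 build the totals from cohort sizes, for example "6 [maximum number anticipated on dose level 3] + 7 [for dose expansion] = 25" in the largest case.

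**The concern.** The usual safety population is everyone exposed to drug, because toxicity does not depend on whether an entry criterion was later found to be unmet. With the eligibility condition, a review of entry criteria after treatment could remove a patient, and that patient's events, from a primary endpoint. It also leaves unclear whether a DLT in a treated but ineligible patient counts in 7.3.

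The second question is the 3+3 denominator. A patient who takes a few doses and then leaves for a reason other than toxicity has been treated and has had no DLT, so a literal count scores that patient as a success for the level. Such miscounting can only favour passing. A pass at level 2 opens ibrutinib 840 mg, and a pass at level 3 makes it the dose to expand.

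**Working it through.** **1. The plan's totals.** The six notes in 14.1 add up as stated: 6+6+10 = 22; 6+3+10 = 19; 6+6+6+7 = 25; 6+6+6+4 = 22; 6+3+6+4 = 19; 6+3+6+7 = 22. Each is a plain sum of cohort sizes, with no allowance for non-evaluable patients.

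**2. Safety set (illustrative counts).** Remove one ineligible patient:
- 2/6 = 33% becomes 1/5 = 20% if that patient had the event, or 2/5 = 40% if not.
- 3/10 = 30% becomes 2/9 = 22% or 3/9 = 33%.

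The largest possible level has 6+10 = 16 patients, so one removal is never negligible.

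**3. DLT counts as written.** The documents give neither a DLT rate nor an early-exit rate, so these are assumptions: true DLT rate p of 40% or 20%; share d leaving cycle 1 early of 10% or 20%; share h of a leaver's DLT risk that is lost, 0.5 or, as an upper bound, 1. If leavers count as DLT-free, the effective rate is q = p(1 − d·h).
- Pass at level 1 or 2 (0/3, or 1/3 then 0/3): f(q) = (1−q)³ + 3q(1−q)⁵.
- Pass at level 3 (at most 1/6): g(q) = (1−q)⁶ + 6q(1−q)⁵.

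For p = 0.4, d = 0.1, h = 0.5: q = 0.4 × 0.95 = 0.38. Then f rises from f(0.40) = 0.216 + 0.093 = 0.309 to f(0.38) = 0.238 + 0.104 = 0.343.

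| Level, p | No leavers | d=10%, h=0.5 | d=20%, h=0.5 | d=10%, h=1 | d=20%, h=1 |
|---|---|---|---|---|---|
| 1–2, 40% | 31% | 34% | 38% | 38% | 45% |
| 1–2, 20% | 71% | 73% | 75% | 75% | 79% |
| 3, 40% | 23% | 27% | 30% | 30% | 38% |
| 3, 20% | 66% | 68% | 70% | 70% | 75% |

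**4. DLT counts with an evaluable rule and replacement.** Every DLT is kept and DLT-free leavers are replaced, so the DLT rate among evaluable patients is r = [(1−d)p + d·p(1−h)] / [1 − d(1 − p(1−h))]. With h = 0.5 and d = 10%:
- p = 0.4: r = 0.38/0.92 = 0.413 and f = 0.289, against 0.309.
- p = 0.2: r = 0.19/0.91 = 0.209 and f = 0.690, against 0.709.

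With d = 20%, f is 0.265 and 0.666.

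**5. Extra patients.** Section 7.3 records three patients at level 2 as of October 2021. At most (6−3) + 6 = 9 escalation slots then remained. 9/0.9 = 10 and 9/0.8 = 11.25, rounded up to 12: 1 to 3 extra patients.

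**The case against.** On the safety set, 14.3.1 says who is included and does not say that nobody else is. The toxicity rule in 2.4.1 refers to each patient without an eligibility filter. Section 5 has eligibility verified before enrolment and 15.6 allows no waivers, so treated ineligible patients should be rare. A reader might infer that the plan sets out to discard toxicity in such patients, or that some have already been dropped; the documents show neither. What stands is that the only section headed as a population rule carries the condition, no other text restores these patients, and 14.3.2 uses a different denominator.

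On the DLT counts, a reader might infer that the plan orders early leavers to be scored as DLT-free. It does not. The MTD definition looks at events before cycle 2, which a leaver never starts, so that patient's status is open and the consequence is inferred from silence. The gap is also narrower than a list of exit reasons suggests. Section 7.1 accepts possible attribution and 10.6.2 allows it even when concurrent disease could explain the event, so many serious illnesses that end cycle 1 would already be DLTs. Adverse event capture for 30 days outlasts a 28-day cycle; what is lost is exposure rather than observation.

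Nor is it right that there is no room for replacement anywhere: a level closed at 0/3 is three below its cap of six. The scenario totals, however, allow for none. Finally, an evaluable rule moves the pass chance slightly the other way. That is true, but the movement is towards caution.

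**Conclusion.** The safety-set point holds on the wording and is the main one: eligibility conditions a primary endpoint, and one removal can shift a rate by several percentage points or more, in either direction. It bites only if a treated patient is later found ineligible.

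The DLT point holds as a secondary gap. With 10% leavers at half risk, the pass chance rises by about 2 to 4 points across levels and the two DLT rates. The larger entries in the table need 20% leavers within one cycle or no DLT risk at all after leaving, and the latter sits poorly with 30-day event capture. A reader might conclude that escalation is seriously biased towards toxic doses; without DLT or exit rates in the documents, that is not supported. The at-most-1-of-6 requirement also buffers the effect, and if level 3 fails, "then an additional 7 patients will be enrolled onto dose level 2 before completing enrollment".

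**What to change.** **Safety set (14.3.1).** Define it as every patient who received any dose of protocol treatment, eligible or not. State that a DLT in any such patient counts in 7.3. This is wording only, since 10.5 already captures all adverse events.

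**DLT-evaluable set (remaining counts at levels 2 and 3).** A patient is evaluable if either:
- a DLT occurs in cycle 1, whatever dose was received; or
- the cycle 1 window is completed without a DLT after a stated minimum share, for example 75%, of the patient's own protocol-assigned cycle 1 doses.

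Assigned doses must include the mandated renal, hepatic and age reductions. If the share were taken in mg of the level's nominal dose, lenalidomide 10 mg for GFR 30–60 (1.2) would be only 10/25 = 40% at levels 2 and 3. Ibrutinib 280 mg for Child-Pugh A (8.1.2) would be 280/560 = 50% or 280/840 = 33%. Those patients could then never be evaluable without a DLT. Doses withheld for treatment-related toxicity should not count as missed. Replace non-evaluable patients at the same level, read the cap of six as six evaluable patients, and restate the totals in 14.1 and 14.2. Patients already counted can be classified from their dosing records; 6.3.4 already calls for a diary.

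**Cost.** About 1 to 3 extra patients over at most nine slots at 10–20% non-evaluable, so the maximum of 25 becomes 26 to 28. Fewer are needed if escalation has advanced since October 2021. Escalation is slightly slower and the rule leans slightly to caution: with 10% leavers at half risk, a level 1–2 pass chance of 29% against 31% at a 40% DLT rate, and 69% against 71% at 20%.

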14.3.2 Statement for Primary Endpoint

The primary endpoint of the dose escalation portion of this phase I study is the MTD. The maximum tolerated dose is defined as the highest dose level among those tested where at most one out of 6 patients develops a DLT prior to the start of their second cycle of treatment and the next highest dose level is such that 2 or more patients among the maximum of 6 patients treated at that dose level developed a DLT prior to the start of their second cycle of treatment.

The primary endpoint of the expansion portion of this phase I study is the objective response rate. The objective response rate is the percent of patients who meet the International Myeloma Working Group Response Criteria for sCR, CR, VGPR, or PR on two consecutive evaluations at least 4 weeks apart among the patients who began study treatment. A 90% binomial confidence interval will be constructed for the overall objective response rate.

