Secondary Objectives	
To determine the following:
 
 1. Progression-free survival (PFS): Time from registration to disease progression or death due to any cause. 2. Overall survival (OS): Time from registration to death due to any cause. 3. Overall Response Rate: Time from start of treatment to objective response 4. Duration of response: Time from documented response to disease progression among those patients whose disease meets the IMWG criteria for disease response
Correlative Science Objectives	To perform select immunologic studies with this combination therapy.
Study Design	
Part 1: Dose Escalation
 
Patients in the dose escalation phase will receive oral treatment with:
 
Ibrutinib: Days 1-28 of every 28-day cycle Lenalidomide: Days 1-21 of every 28-day cycle Dexamethasone: 40 mg for patients <75 at the time of registration 20 mg for patients ≥ 75 at registration on Days 1, 8, 15 and 22 of every Cycle. One cycle is 28 days.
 
Starting doses of ibrutinib and lenalidomide will be assigned at the time of registration. A minimum of 2 or a maximum of 6 patients will be accrued to a given dose level. Doses will not be escalated in any individual patient. If none of the first 3 patients treated at a given dose level develops a DLT during the first cycle of treatment, enrollment to the dose level will be closed and enrollment will reopen at next higher dose level. If there are no other higher dose levels to be tested, three additional patients will be enrolled at the current dose level to confirm MTD. If one of the first 3 patients treated at a given dose level develops a DLT during the first cycle of treatment, three additional patients will be enrolled onto the current dose level. If, at any time in the enrollment of these 3 additional patients, a patient develops a DLT, enrollment will be closed to this dose level. Enrollment will be reopened to the next lower dose level if fewer than 6 patients have been treated at that dose level. If none of these 3 additional patients develops a DLT during the first cycle of treatment, enrollment to this dose level will be closed and enrollment will reopen at next higher dose level. If

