2.2. Secondary Objectives

The secondary objectives of this study are:

1. To determine progression-free survival (PFS)
2. To determine overall survival (OS)
3. To determine duration of response
4. To determine overall response rate (ORR)

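### Response rate is primary for the expansion in Section 14.3.2 but secondary elsewhere, and its 90% interval is not tied to the patients at the MTD

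*Combined protocol and SAP*

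**What the plan says.** **Status.** Section 14.3.2 gives the two parts of the study different primary endpoints: the MTD for escalation, and for the expansion, "The primary endpoint of the expansion portion of this phase I study is the objective response rate". Section 2.2 lists ORR as the fourth secondary objective. Section 2.4.1 lists it third among the secondary endpoints, with MTD and safety profile as the two primary ones. The synopsis also lists it as secondary, and words it as a time rather than a proportion: "Overall Response Rate: Time from start of treatment to objective response".

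**Denominator and interval.** Section 14.3.2 takes the percentage "among the patients who began study treatment" and adds: "A 90% binomial confidence interval will be constructed for the overall objective response rate". Patient Evaluability (Section 14.3.1) sets the population for safety and clinical outcomes: "All patients meeting the eligibility criteria who have signed a consent form and have begun treatment will be included in the analysis". None of these sentences names a dose level or limits the interval to the expansion. The section on secondary endpoints, also numbered 14.3.1, tabulates responses for each dose level, without an interval.

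**Expansion size.** Sections 7.3 and 14.1 make it depend on the MTD: 10 patients at level 1, 7 at level 2, and 4 at level 3 ("then an additional 4 patients will be enrolled onto dose level 3 before completing enrollment"). Section 1.2 and the opening of Section 14.1 give a fixed 10.

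**The concern.** An endpoint that is primary in the statistics section and secondary in the objectives can be reported under either label with the protocol as authority. The open denominator matters more. The expansion is meant partly to show anti-tumour activity at the MTD. An interval over all treated patients mixes regimens that differ in ibrutinib or lenalidomide dose. An interval over the expansion alone sets aside patients assigned to the same dose level during escalation. Choosing between the two after the responses are known would be a post hoc choice of estimand.

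**Working it through.** **Step 1: the plan's own totals.** The counts come from the notes in Section 14.1, which take 6 patients at level 1 and the maximum anticipated at level 3. All six totals reproduce exactly.

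| Outcome | Plan's sum | MTD level | Expansion | Assigned to MTD level | Share of all treated |
|---|---|---|---|---|---|
| Level 2 too toxic, 6 treated there | 6+6+10 = 22 | 1 | 10 | 6+10 = 16 | 16/22 = 73% |
| Level 2 too toxic, 3 treated there | 6+3+10 = 19 | 1 | 10 | 6+10 = 16 | 16/19 = 84% |
| Level 3 too toxic, 6 at level 2 | 6+6+6+7 = 25 | 2 | 7 | 6+7 = 13 | 13/25 = 52% |
| Level 3 too toxic, 3 at level 2 | 6+3+6+7 = 22 | 2 | 7 | 3+7 = 10 | 10/22 = 45% |
| Level 3 tolerated, 6 at level 2 | 6+6+6+4 = 22 | 3 | 4 | 6+4 = 10 | 10/22 = 45% |
| Level 3 tolerated, 3 at level 2 | 6+3+6+4 = 19 | 3 | 4 | 6+4 = 10 | 10/19 = 53% |

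Pooling all treated patients therefore mixes two levels in the first two outcomes and three in the other four.

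**Step 2: interval by denominator.** The plan says binomial without naming a method, so I assume the two-sided exact (Clopper-Pearson) interval. For x responders of n, the lower limit is the 5% quantile of Beta(x, n−x+1) and the upper limit is the 95% quantile of Beta(x+1, n−x). I take x as close to n/2 as possible. Widths come from unrounded limits.

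| x/n | Exact 90% interval | Width (points) |
|---|---|---|
| 2/4 | 9.8–90.2% | 80.5 |
| 4/7 | 22.5–87.1% | 64.6 |
| 5/10 | 22.2–77.8% | 55.5 |
| 6/13 | 22.4–71.3% | 48.9 |
| 8/16 | 27.9–72.1% | 44.3 |
| 10/19 | 32.0–72.6% | 40.6 |
| 11/22 | 31.1–68.9% | 37.7 |
| 12/25 | 30.5–65.9% | 35.3 |

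**Step 3: like-for-like comparison within each MTD level**, expansion only against everyone assigned to that level.

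- Level 3: n from 4 to 10, width 80.5 to 55.5 points.
- Level 2: n from 7 to 10 or 13, width 64.6 to 55.5 or 48.9 points.
- Level 1: n from 10 to 16, width 55.5 to 44.3 points.

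The observed rates differ slightly where n is odd (4/7 is 57%, 6/13 is 46%), so the level 2 figures are approximate. Wilson intervals are narrower but move the same way: at level 3, 18.2–81.8% (2/4) becomes 26.9–73.1% (5/10).

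**Step 4: what pooling could do to the estimate.** The plan gives no response rates by level. Assume, for illustration only, 20%, 35% and 50% at levels 1, 2 and 3. With level 3 as MTD and 22 patients, the pooled expectation is (6×0.20 + 6×0.35 + 10×0.50)/22 = 8.3/22 = 37.7%, about 12 points below the MTD rate. With level 2 as MTD and 25 patients it is (6×0.20 + 13×0.35 + 6×0.50)/25 = 8.75/25 = 35%, no shift. Equal rates at all levels also give no shift. So the narrower pooled intervals in step 2 may or may not be centred on the recommended regimen.

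**The case against.** The other side has a good deal to say.

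- *The plan pools three dose levels.* A reader might infer this from the word overall in the interval sentence. But Overall Response Rate is the endpoint's name in the synopsis and Section 2, and the paragraph opens with the expansion. Pooling is permitted by the text, not established, and two of the six outcomes involve only two levels.
- *The estimate rests on 4 patients.* That needs both level 3 as the MTD and the expansion-only reading, and the text also gives a fixed expansion of 10.
- *Escalation patients at the MTD are discarded.* No section says so. Patient Evaluability would include them; their use with the expansion is simply unspecified.
- *Responses are already tabulated by dose level.* True, so the count at the MTD is planned. Only an interval for it is missing.
- *The label changes no inference.* Also true: there is no null rate, target rate, alpha, power or decision rule for ORR. Section 14.1 justifies the expansion numbers by reaching 10 patients with biospecimens at the MTD, not by ORR precision.
- *Patients at one level are not all on one dose.* Sections 1.2 and 8.1.2 provide for reduced starting doses in renal and mild hepatic impairment. This stands, and it means the analysis set must be defined by assigned level.
- *Combining escalation and expansion is a choice.* It is. The MTD is selected on cycle 1 DLTs rather than on response, so adding those patients should cost little in bias unless the two are strongly related.

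What survives is the conflict of status and the unnamed population for the interval.

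**Conclusion.** The point holds in limited form. Section 14.3.2 contradicts Section 2 and the synopsis on whether ORR is primary, and does not say whose response rate the 90% interval describes. The permitted denominators run from 4 to 25, with widths near 50% response from about 80 to 35 points. The wider intervals omit MTD patients, and the narrower ones may include other regimens. Using everyone assigned to the MTD level would gain roughly 25 points over expansion only at level 3, 9 or 16 at level 2, and 11 at level 1.

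These figures rest on the Section 14.1 branch counts, an exact two-sided interval and a response rate near one half. The documents do not support a claim that the planned analysis is invalid, or that ORR must be secondary: no test depends on the label, and either status could be made consistent.

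**What to change.** 1. In Section 14.3.2, state that ORR and its 90% interval are estimated in all eligible treated patients assigned to the MTD dose level, escalation plus expansion. Define the set by assigned level, so that a reduced starting dose does not make membership ambiguous. Name the method (exact) and give the expected precision for n = 10, 13 or 16.
2. Keep the other dose levels in separate tabulations, as the secondary-endpoint section already plans.
3. Give ORR one status throughout. Either call it secondary in Section 14.3.2, matching Section 2 and the synopsis, or amend those sections to name it the primary endpoint of the expansion. At the same time, reword the synopsis entry as a proportion.
4. Reconcile the fixed expansion of 10 in Section 1.2 and the opening of Section 14.1 with the 4, 7 or 10 in Sections 7.3 and 14.1.

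The cost is wording only: no extra patients, visits or data. The change should be made before response data at the MTD are reviewed.
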